4D. A complete copy of the funding proposal or contract is attached.  Attached, please specify title : Improving Attendance in Community Wise
4E. Funding Agency Official To Be Notified of IRB Approval (if Applicable) Name: N/A Agency: E-mail: Phone:

Section 5. CONFLICTS OF INTEREST

Please indicate below whether any investigators or members of their immediate families have any of the following. If the answer to any of the following items is yes, please submit the University of Illinois approved conflict management plan. If you have any questions about conflicts of interest, contact [contact].

5A. Financial interest or fiduciary relationship with the research sponsor (e.g. investigator is a consultant for the research sponsor).  Yes  No
5B. Financial interest or fiduciary relationship that is related to the research (e.g. investigator owns a startup company, and the intellectual property developed in this protocol may be useful to the company).  Yes  No
5C. Two or more members of the same family are acting as research team members on this protocol.  Yes  No

Section 6. SUMMARY & PURPOSE OF RESEARCH

Rates of alcohol and substance misuse (ASM) in low-income, predominantly African American communities (from here on marginalized communities) are similar to the general population.¹ However, ASM has greater consequences (e.g., higher incarceration and HIV/HCV infection rates) for residents in these communities. While the etiology underpinning this inequity is complex, the root cause of these issues has been traced to social determinants of health (SDH; e.g., stigma; poverty; access to education, housing, and employment).^{2,3}

Funded by the National Institute for Minority Health Disparities (NIMHD 5R01MD010629),⁴ in partnership with the Critical Consciousness Collaborative Board (3CB),⁵ we developed Community Wise (CW), a multi-level manualized behavioral intervention to decrease ASM frequency in a population of self-identified men with histories of substance use disorder (SUD) and incarceration in Essex County, NJ, U.S. The 3CB was founded in 2010 and developed and pilot-tested the original CW. To attain this goal, our team used the multiphase optimization strategy (MOST),⁶ and were guided by community based participatory research (CBPR) principles to develop and optimize CW. MOST is an innovative methodological framework that employs experimental designs to engineer efficient and effective behavioral interventions. MOST guided

the optimization of CW with delivery cost of less than \$2,000 per intervention cycle serving up to ten individuals simultaneously (this was the Medicaid allowable reimbursement cost for SUD group treatment services in 2015).⁷ Clinical trial results showed larger ASM reduction (Cohen's $d=-2.22$, $P=0.067$) in the optimized CW group. Unfortunately, attendance across the 15 intervention sessions was low (only 15% of participants attended 50% of the sessions) and a limitation to the study. Low attendance was due to the intervention's closed group format, the study's randomization strategy, and instability of the study's population (homelessness, poverty).

In order to improve upon our positive results and to test the intervention with participants who identify as female and do not have a history of incarceration, we propose a pilot study to: 1) identify strategies to improve attendance and reduce ASM, and 2) to test feasibility and acceptability of CW among people with a history of SUD living in marginalized communities. We will achieve these aims by conducting a 2^3 full factorial experiment. This pilot study will strengthen our application for an R01 grant to test CW's effectiveness against standard of care. This pilot will help us identify efficient strategies for improving attendance and, hence, maximize the interventions' effect in reducing ASM. As a highly efficient experimental design, a full factorial experiment will maximize study power and allow us to examine the individual and interactive contributions of each intervention delivery strategy on intervention attendance. MOST will inform which strategies will be retained, thus minimizing waste of resources. The current proposed research will also be conducted in partnership with the 3CB. As our primary individual level outcome, we will use number of sessions attended to pursue the following aim:

Study AIM: To test intervention delivery strategies that effect adequate attendance in CW interventions and marked reduction in ASM. We will test if different intervention delivery strategies will result in a clinically important intervention attendance with a minimum of 50% of participants attending at least 50% of the intervention. We will also compare the effect of different strategies on reducing ASM. Intervention delivery strategies include: 1) Recruiting individuals under supervision (those on parole, drug court, probation, or methadone maintenance); 2) Incentivizing intervention attendance; and 3) Delivering the intervention in an open group format. We will also compare intervention satisfaction measures between intervention strategies.

We will expand eligibility criteria to include women and people with SUD living in marginalized communities who have not been previously incarcerated. While women comprise a smaller percentage of people with SUD, they experience significant barriers to SUD treatment.⁹ Our pilot study showed that women started the CW intervention with worse outcomes when compared to men but had significantly higher reductions of ASM.¹⁰ While the original CW intervention was developed with and for formerly incarcerated people, it addresses concepts that are relevant to all people with SUD living in marginalized communities. Hence, the 3CB has recommended that we expand our eligibility criteria to reach a more diverse group of people. Our 2^3 full factorial design will examine change in attendance (N=128). Data will be collected at baseline and three months post-baseline. This study will impact public health as it will improve the potency of an optimized multi-level intervention adaptable to address different health inequities.

**6B. Indicate if your research includes any of the following:**

- Secondary data (use of data collected for purposes other than the current research project)
- Data collected internationally (include [International Research Form](#))
- Translated documents (include [Certificate of Translation Form](#) and translated documents)
- Research activities will take place at Carle (include documentation (email or letter) from Carle stating that the review of your [Research Services Request Form](#) is complete)

6C. Letters of support from outside institutions or entities that are allowing recruitment, research, or record access at their site(s) are attached. Yes Not Applicable

Section 7. PROCEDURES

7A. Select all research methods and/or data sources that apply.

- Surveys or questionnaires, *select all that apply:* Paper Telephone Online
- Interviews
- Focus groups
- Field work or ethnography
- Standardized written, oral, or visual tests
- Taste or smell testing
- Intervention or experimental manipulation
- Exercise and muscular strength testing
- Noninvasive procedures to collect biological specimens (e.g., hair and nail clippings, saliva, etc.)
- Noninvasive procedures to collect physiological data (e.g., physical sensors, electrocardiography, etc.)
- Procedures involving radiation
- Recording audio and/or video and/or taking photographs
- Recording other imaging
- Materials that have already been collected or already exist, *specify source of data:*
- [HIPAA-protected data](#)
- [FERPA-protected data](#)
- [GDPR-protected data](#)
- Other, *please specify:*

7B. List all testing instruments, surveys, interview guides, etc. that will be used in this research.

Drafts or final copies of all research materials are attached. Yes

7C. List approximate study dates. Upon IRB Approval – April 31, 2024

7D. What is the duration of participants' involvement? Participants will complete a 15 minutes study orientation session and two 30 minutes online surveys. They will also be asked to attend 8, two-hour long weekly intervention sessions

7E. How many times will participants engage in research activities? Two times for study activities and 8 times for the intervention.

7F. Narratively describe the research procedures in the order in which they will be conducted.

People interested in the study will call the study's number. A trained master's level clinician will conduct a brief phone screening to obtain self-reported eligibility on SUD, age, contact information, and whether they are currently under supervision. We will have recruitment quotas of 64 people based on self-reported gender (self-identified as men or woman) and supervision status. Intervention groups will be gender specific following recommendations from the literature and our previous CW pilot study. Phone screened participants will be invited to attend an in-person group orientation session to learn about the study, including randomization procedures and the different forms of CW delivery they may receive. Those interested will be invited to complete the baseline survey online in RedCAP. The survey will include a screening informed consent and an eligibility screen with a computerized Global Appraisal of Individual Needs-Substance Problem Scale (GAIN-SPS).³⁵ Those who are eligible and agree to the procedures will be consented and invited to complete the baseline assessment. Follow-ups will be completed online using RedCAP three months post baseline. Baseline and follow-up will include questions about SUD treatment services received over the past 3 months, the Timeline Follow Back questionnaire to measure alcohol, cannabis, cocaine, opioid, and heroin use in the past 30 days, and demographics. Follow ups will also include intervention satisfaction measures and questions about intervention attendance. Surveys will take 30 minutes to complete. Participants will receive \$20 for baseline and \$30 for follow up assessment. Intervention attendance will be recorded weekly in RedCAP by the peer facilitator. After the baseline assessment, participants will be asked to provide extensive locator information, including formal and informal contacts who can reach the participant in a variety of contingencies. Computer generated randomly permuted blocks will be used to assign participants into one of eight experimental conditions. Randomization will occur in Redcap immediately after completing the baseline and be stratified by gender. The research assistant will call participants after randomization to schedule the group's start date. The attached study flowchart summarizes all study procedures.

Intervention: Community Wise (CW) includes two, two-hour long group-building sessions and six two-hour long active components sessions. Sessions are delivered weekly by a trained peer facilitator. Group-building sessions create a safe space where participants can discuss racism, sexism, classism, and histories of marginalization in the context of ASM and drug traffic. Based on the optimization study, we identified two active components that increase critical consciousness and, thus, health inequities related to ASM. These include the Critical Dialogue (CD), prompted by thematic images (see table below) and aims to help participants develop a deeper understanding of how marginalizing processes (e.g., systematic stigma; feelings of rage as victims of discrimination) impact their lives and behavior; and 2) Capacity Building Projects (CBP) designed to create collaborative efforts to overcome and dismantle marginalizing processes by building positive social and organizational relationships and community capacity through the development and implementation of community projects aiming to address social determinants of health. Our study detected no difference when the intervention was delivered by peer facilitators versus licensed facilitators. Trained peer facilitators can deliver the intervention at a lower cost and benefit from a new employment opportunity.

Participant tracking: Most of our participants earn less than 10,000 yearly and many will likely be homeless. While they share phone numbers and email addresses with the study team, they may be

unable to answer their pre-paid phone when they run out of minutes or they may not be able to access a computer easily. Thus, collecting extensive tracking information is critical to make sure we can reach them. We ask for alternative contact numbers, places where they hang out (especially important for those who are homeless), and social media accounts to maximize our chances to find them in case we lose touch. We have used this approach in all our previous studies without any problems. When collecting this information, the RA explains to participants why we ask this information and asks them if it is ok with them. We also ask participants what they would like us to say if we are looking for them. We follow the participants' instructions and they can refuse to offer alternative contacts or grant permission for us to look for them at any time during the study.

Section 8. PERFORMANCE SITES TO INCLUDE INTERNATIONAL, SCHOOL, AND COLLABORATIVE STUDIES

8A. List all research sites for the protocol. For non-University of Illinois at Urbana-Champaign sites, describe their status of approval and provide contact information for the site. If the site has an IRB, note whether the IRB has approved the research or plans to defer review to the University of Illinois at Urbana-Champaign.

Performances Sites

#1	Comprehensive Behavioral Health Center [name], They do not have an IRB and will defer to UIUC
#2	
#3	

If there are additional performance sites, include them on an attachment and check here:

8B. Is this a multi-center study in which the Illinois investigator is the lead investigator, or the University of Illinois at Urbana-Champaign is the lead site? Yes No

If yes, answer 8C and 8D. If no, proceed to Section 8E.

8C. Who is the prime recipient of funding, if funded? N/A

8D. What is the management and communication plan for information that might be relevant to the protection of research subjects (e.g. unanticipated problems involving risks to subjects, interim results, and protocol modifications)? N/A

8E. If subjects will be recruited from Illinois public or private elementary or secondary schools, additional deadlines and procedures may apply. Criminal background clearances might be required. Special consideration must be given to the exclusion of protected populations. Please contact the [School University Research Relations \([contact]\)](mailto:School University Research Relations ([contact])) for more information. Select one: Illinois schools **will** be used Illinois schools **will not** be used

Section 9. SUBJECT ENROLLMENT GOAL & EQUITABLE SELECTION OF SUBJECTS

9A. For each performance site, indicate the estimated total number of participants.

Performance Site	# Male	# Female	Total
------------------	--------	----------	-------

#1	Comprehensive Behavioral Health Center [name], approved IRB for another study	64	64	128
#2				
#3				
TOTALS				
If additional performance sites are included on an attachment, check here: 				
9B. Select all participant populations that will be recruited.				
Age:				
 Adults (18+ years old)  Minors (\leq 17 years old)  Specific age range, please specify:				
Gender:				
 No targeted gender (both men and women will be recruited/included)  Targeted gender, please indicate:  Men/boys  Women/girls  Other, please specify:				
Race/Ethnicity:				
 No targeted race or ethnicity (all races and ethnicities will be recruited/included)  Targeted race or ethnicity, please specify:				
College Students:				
 No targeted college population  UIUC general student body  Targeted UIUC student population, provide the instructor or course information, name of the departmental subject pool, or other specific characteristics:  Students at institution(s) other than UIUC, please specify:				
Any research with students on UIUC's campus needs to be registered with the Office of the Dean of Students .				
Other:				
 Inpatients  Outpatients  People who are illiterate or educationally disadvantaged  People who are low-income or economically disadvantaged  People with mental or cognitive disabilities or otherwise impaired decision-making capacities  Adults with legal guardians  People who are non-English speaking  People with physical disabilities  Pregnant or lactating women, human fetuses, and/or neonates  Prisoners or people with otherwise limited civil freedoms  Other, please specify:				
9C. Describe additional safeguards included in the protocol to protect the rights and welfare of the populations selected above.				

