To test the objective 'What combination of interventions was associated with higher attendance?', we used a logistic regression model to test the association of group type (open vs closed), incentivizing intervention attendance (incentive vs not) and surveillance (under surveillance vs not) with the outcome of attending 50% of sessions or more (vs not). The logistic regression model included main effects, as well as all 2-way interactions and a 3-way interaction using multiplicative terms. The model was adjusted for job search status, sex, race and ethnicity, marital status income, number of days paid in the past 30 days, and employment status. Parameter estimates (coefficients) and their standard errors were reported. Since the outcome for logistic regression model is the log odds of attending 50% or more sessions, parameter estimates (regression coefficients) represent the change in the odds of the outcome on the log scale for a one-unit change in the independent variable (or at one level compared to its referent if continuous). Thus, parameter estimates were transformed by taking the exponent to facilitate interpretation as odds ratio. Exponentiated coefficients are interpreted as the difference in the likelihood (odds) of achieving the outcome between those who received an intervention component compared to those who did not receive it, collapsing (averaging) over levels of the other components and controlling for covariates. To calculate percent change, exponentiated coefficients are compared to the value of one (one means no difference). A value that is greater than one or less than one, indicates that the outcome is more likely or less likely to occur, respectively. Thus, we subtract one from the exponentiated regression coefficient to obtain the magnitude of change in the outcome, and when multiplied by 100 it is a percent change in the outcome.

To test the objective 'Does higher attendance result in less ASM use?' we employed a generalized multiple regression model testing the association of attendance rates (continuous variable), incentivizing intervention attendance (incentive vs not), surveillance (under surveillance vs not) and their 2-way interaction with the outcome of percent of ASM at follow up, adjusting for demographic characteristics and percent of ASM at baseline. We analyzed the intervention components using effect coding (1 vs -

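### Follow-up is fixed at three months after baseline but the wait for the first session is not bounded, so the attendance rate in the ASM model may include sessions held after the outcome

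*Protocol*

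**What the plan says.** **Timing of assessment.** Protocol Section 6: "Data will be collected at baseline and three months post-baseline". Section 7F repeats it: "Follow-ups will be completed online using RedCAP three months post baseline". No visit window is given.

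**Timing of the sessions.** Section 7D: "They will also be asked to attend 8, two-hour long weekly intervention sessions". Section 7F: "Randomization will occur in Redcap immediately after completing the baseline and be stratified by gender", and then "The research assistant will call participants after randomization to schedule the group's start date". The supplied text gives no maximum wait, no minimum group size and no rule for a group still running at three months. Section 7F refers to an attached flowchart, which is not in that text.

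**Who can form a group.** Section 7F: "Intervention groups will be gender specific following recommendations from the literature and our previous CW pilot study". Format is one of the three experimental factors; the SAP lists it as "group type (open vs closed".

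**Measurement and analysis.** Under Section 7F the facilitator records attendance weekly, with no stated cut-off at follow-up, and ASM is recalled over the previous 30 days. For the question whether higher attendance leads to less ASM, the SAP fits a regression described as "testing the association of attendance rates (continuous variable" with incentive, supervision status and interaction terms, adjusted for baseline ASM and demographics. It sets no date limit on the sessions counted, and it leaves group type out of this model.

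**The concern.** The follow-up clock starts at baseline, while the programme starts on a date fixed later. Nothing in the visible text ensures that the programme has finished when ASM is measured.

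The SAP's question is causal in form. A session held after the ASM assessment cannot have changed the answer to it. Counting such sessions misstates the dose received before the outcome, and it allows reverse influence, because substance use around the follow-up date may affect whether someone attends afterwards. The direction of any distortion of the slope cannot be told from the documents.

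The wait could plausibly differ by format. Members of a closed group normally begin together, an open group can admit people as they come, and gender-specific groups draw on a smaller pool. With group type left out of the ASM model, nothing there would absorb such a difference.

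**Working it through.** The plan gives no figure to reproduce, so the check is calendar arithmetic followed by an illustration under stated assumptions.

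**Inputs from the documents.** Follow-up three months after baseline, taken as day 91 (84 to 92 tested). Eight weekly sessions. N = 128, 64 per gender. Two formats.

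**Step 1: longest wait that is safe.** First to last session: 7 × 7 = 49 days. All eight sessions fall on or before follow-up if the wait is at most 91 - 49 = 42 days (35 if follow-up is on day 84, 43 if on day 92).

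**Step 2: sessions held by day 91, by wait.**

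| Wait from baseline to first session | Sessions held by day 91 |
|---|---|
| up to 6 weeks | 8 |
| 7 weeks | 7 |
| 8 weeks | 6 |
| 10 weeks | 4 |
| 12 weeks | 2 |

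Example: a participant whose group starts at week 10 attends two of the four sessions held by follow-up and all four held later. The full rate is 6/8 = 75%; the part that precedes the outcome is 2/8 = 25%.

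**Step 3: how many might wait longer than 42 days.** The documents give neither accrual rate nor group size for this trial; the earlier optimisation study served at most ten people at once. Assume that closed groups do wait to fill, that half of each gender is assigned to closed groups, and that groups mix incentive and supervision status. A group of g then needs 2g randomisations of one gender.

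- Steady accrual: fill time = accrual days × 2g/64; share waiting over 42 days = 1 - 42/fill time, or 0 if the fill time is 42 days or less.
- Groups of 8, accrual of 6, 9 or 12 months (182.5, 273.75 or 365 days): fill times 45.6, 68.4 and 91.25 days; shares 8%, 39% and 54%.
- Groups of 7, 6 months: 182.5 × 14/64 = 39.9 days, so 0%. Groups of 8 also give 0% if accrual takes no more than 42 × 64/16 = 168 days.
- Groups of 10, 12 months: 365 × 20/64 = 114 days, so 63%. This is the extreme of the simple formula.
- Simulated random arrivals, using each member's own wait, accrual of 26 to 52 weeks and groups of 5 to 10: 2% to 53%.

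**Step 4: finer splitting.** In the same simulation the share is 18% to 72% if groups are also split by incentive, and 44% to 76% if split by all eight conditions and gender (groups of 5 or 8).

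**Step 5: whole sample.** If open groups start promptly, halve the figures. For groups of 8 they become 4%, 19% and 27%. The mean number of sessions after follow-up per closed-group member is then about 0.1, 0.9 and 2.2 of 8.

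**The case against.** The strongest reply is that the problem is conditional. Thirteen weeks against an eight-session programme leaves six weeks of slack, and no passage shows that anyone waited longer. Candidates attend a group orientation before baseline, so randomisations may come in batches, which shortens filling. The unseen flowchart might contain a start rule. All of this stands, and it is why the size is given as a range that includes zero.

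Several stronger readings are tempting, but the documents do not support them:

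- *Closed groups have to wait to fill.* This is an inference from the format. The protocol names the closed format as one cause of low attendance in the previous trial but does not mention waiting.
- *The open-versus-closed comparison of ASM is confounded by timing.* The protocol's aim does mention comparing strategies on ASM and satisfaction. The SAP's ASM model omits group type, however, and the SAP describes no satisfaction analysis.
- *The 30-day recall should lie wholly after the last session.* That would need a first session within 91 - 30 - 49 = 12 days of baseline, but nothing in the plan requires it.
- *Follow-up should be timed from the first session.* A fixed interval from baseline gives every randomised participant the same elapsed time, and a wait caused by the format is arguably part of its effect. Re-timing would make the baseline-to-follow-up interval vary by format, and adjusting for that interval means adjusting for something that happens after randomisation.

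What the reply does not answer is the counting rule: the SAP does not say how a session held after follow-up is treated.

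**Conclusion.** The concern holds in a conditional form. Follow-up is tied to baseline, the wait for the first session is not bounded in the visible text, and the ASM model places no date limit on attendance. Any first session after about day 42 therefore puts sessions after the outcome into the exposure.

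The share affected is unknown. With 6 to 12 months of accrual, groups of about 5 to 10 and splitting by gender and format only, it is roughly 0% to 54% of closed-group members (63% at the extreme of the simple formula), and about half that across the sample. It is higher if groups are condition-specific. These figures rest on assumed accrual and group size and on closed groups waiting to fill. No bias in the attendance-ASM slope has been quantified, and the primary attendance outcome is not shown to be affected.

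**What to change.** 1. In the ASM model, define attendance as sessions attended on or before the participant's actual follow-up date, divided by 8, and set it to 0 if the group had not started. The fixed denominator matters: dividing by sessions held so far would score 1 of 1 the same as 8 of 8 and would be undefined for a group not yet started.
2. Report baseline-to-first-session time by group format, with the number of participants who had sessions after follow-up. If there were none, this closes the point.
3. Keep the full attendance rate as a sensitivity analysis.
4. Leave the primary attendance outcome and the follow-up schedule as they are.

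**Cost.** A few lines in the SAP, one table and one extra model run, provided that session and survey dates were kept; both attendance and surveys go into RedCAP. The SAP is dated 6/1/2025 and written in the past tense, and the protocol's study dates end in April 2024, so this is an analysis and reporting change. The downside is that the exposure in this model differs slightly from the attendance rate used elsewhere: it measures dose received by the outcome, so a late starter scores low partly because fewer sessions had been offered.
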